10.2 Determination of Sample Size

For sample size estimation, we used the EQ-5D-5L score, which is required to calculate the ICER. A 2sided two-sample means test (Satterthwaite's t test assuming unequal variances) was applied. Alpha was set at 0.05 and the power at 0.90.

The existing control group (42 working patients with RSI arthroplasty) shows a mean EQ-5D-5L score of 0.91 (SD 0.09) at 1 year. From our DSG-registry, preliminary data of the 1-year follow-up indicate a mean EQ-5D-5L score of 0.96 (SD 0.05) of patients with a Touch® implant.

With the given sample size of 42 in the control group, 68 patients have to be included in the experimental (Touch®) group. Accounting for a dropout rate of 15%, we aim to include 80 patients in the Touch® group.

10.3 Statistical criteria of termination of trial

In this study, there is no statistical criteria for the termination of the trial.

10.4 Planned Analyses

10.4.1 Datasets to be analysed, analysis populations

The dataset to be analysed includes all eligible and enrolled patients that will be operated and scheduled to receive the Touch® prosthesis.

For the sensitivity analysis as well as the analysis of the secondary outcomes, all eligible and enrolled patients that effectively received the respective intervention according to the CIP will be included.

10.4.2 Primary Analysis

Quality of life

The EQ-5D-5L responses will be converted into utilities ranging from -0.66 (lowest QoL) to 1(highest QoL) according to the German value set [34]. The change in quality of life measured by the EQ-5D utility index from before to 1 year after surgery will be analysed by the paired t-test. Sample size will be sufficient to waive the requirement for Normal distribution of the outcome parameter.

Only one look at the data will be performed at the end of follow-up and significance level will be set at 5%.

Cost-utility analysis / Quality-Adjusted Life Years (QALYs)

A population preference-based value index from Germany will be used to calculate Quality-Adjusted Life Years (QALYs) for each patient. The gain in QALYs of Touch patients compared to RSI patients will be evaluated.

QALYs will be calculated as "utilities" multiplied with "time units" under this utility. Then, a cost-utilityratio will be calculated as: Additional costs per additional QALY (Quality adjusted life year). The incremental cost-utility ratio will be calculated as the difference in costs over the difference in Quality-Adjusted Life Years (QALYs) between both interventions [28].

> Cost _{Touch®} - Cost _{RSI} Arthroplastik QALYS_{Touch®} - QALYS_{RSI} Arthroplastik

Sensitivity analyses will be performed considering:

- Different assumptions of gain in QALYs
- Different assumptions for calculation of indirect costs (productivity losses)
- Different assumptions about the direct medical costs.

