10 STATISTICAL METHODS

10.1 Hypothesis

Ho: Null hypothesis

The CMC I arthroplasty using the Touch® implant is not more cost-effective compared to the RSI arthroplasty in terms of an acceptable ICER.

H1: Alternative Hypothesis

The CMC I arthroplasty using the Touch® implant is more cost-effective than the RSI arthroplasty in terms of an acceptable ICER.

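### The only significance test in the primary analysis is a within-Touch paired t-test, while the 90% power belongs to a two-sample Touch-versus-RSI test that no analysis section contains

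*Protocol*

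**What the plan says.** **Hypothesis (section 10.1).** The alternative is comparative: Touch "is more cost-effective than the RSI arthroplasty in terms of an acceptable ICER".

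**Sample size (section 10.2, repeated in the synopsis).** The calculation is between groups: "A 2sided two-sample means test" in its unequal-variance form. The error rates are fixed: "Alpha was set at 0.05 and the power at 0.90". The RSI input is "The existing control group (42 working patients with RSI arthroplasty) shows a mean EQ-5D-5L score of 0.91 (SD 0.09) at 1 year". The Touch input, from registry data, is a "mean EQ-5D-5L score of 0.96 (SD 0.05) of patients with a Touch® implant". The result is "With the given sample size of 42 in the control group, 68 patients have to be included in the experimental" group, raised to 80 for 15% dropout.

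**Primary analysis (section 10.4.2).** Under quality of life, the change is "measured by the EQ-5D utility index from before to 1 year after surgery will be analysed by the paired t-test". The statistical paragraph of the synopsis names the same paired test. The gain in QALYs of Touch over RSI is to be evaluated, and the ICER is computed as a ratio with sensitivity analyses on its assumptions.

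**Other analysis text.** Section 10.4.1 defines the analysis dataset as enrolled patients scheduled for the Touch prosthesis. Section 10.4.3 gives descriptive summaries, a mixed model with an effect of time, and an ICER on the pain score. None of these sections contains a two-sample test.

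**The concern.** The protocol powers one test and plans another. The powered test compares Touch with RSI at 1 year. The planned test compares Touch patients with themselves before surgery. A pre-to-post improvement after CMC I surgery is expected with either operation: section 3.3 itself refers to good outcomes and a gain in quality of life after surgical treatment. A significant paired result would therefore be compatible with Touch being better than, equal to or worse than RSI.

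The stake is how the result is read. The rationale (section 3.1) is to build an argument to insurers that Touch is worth its higher price compared with RSI. If the plan is followed literally, the named p-value in the primary analysis says nothing about that comparison. The report could nevertheless describe the study as having had 90% power for its primary analysis, which would be untrue of the test performed.

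**Working it through.** **1. Reproduce the plan's figure.** Inputs, all from section 10.2: RSI n = 42, mean 0.91, SD 0.09; Touch mean 0.96, SD 0.05; two-sided alpha 0.05; target power 0.90.

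- Difference: 0.96 − 0.91 = 0.05.
- Variances of the means with 68 Touch patients: 0.09²/42 = 0.00019286 and 0.05²/68 = 0.00003676.
- SE = √(0.00019286 + 0.00003676) = 0.01515.
- Noncentrality = 0.05/0.01515 = 3.30.
- Satterthwaite df = (v₁ + v₂)² / (v₁²/41 + v₂²/67) = 56.9.
- Power from the noncentral t: 0.9003 at 68, 0.8997 at 67. The smallest Touch group reaching 0.90 is 68, as stated.
- Dropout: 68/(1 − 0.15) = 80, as stated.
- If all 80 are evaluable against 42, power is 0.907.

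Section 10.2 is therefore correct for the test it names.

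**2. Set the powered test beside the planned test.**

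| | Powered (10.2, synopsis) | Planned (10.4.2, synopsis) |
|---|---|---|
| Test | two-sample, unequal variances | paired |
| Contrast | Touch minus RSI | after minus before, within patient |
| Variable | EQ-5D-5L at 1 year | change to 1 year |
| Uses RSI data | yes | none named; the 10.4.1 dataset is Touch only |
| Inputs given | both means and both SDs | no baseline mean, no SD of change |

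**3. Can the 90% be carried over to the paired test?** No. Its power depends on (mean change)/(SD of change), and the protocol gives neither. With 68 pairs, 90% power requires a standardised change of 0.40. Under assumed values:

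| Assumed mean change | SD of change 0.05 | 0.10 | 0.15 | 0.20 |
|---|---|---|---|---|
| 0.05 | >99.9% | 98% | 77% | 53% |
| 0.10 | – | – | >99.9% | 98% |

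The range is too wide to support any single figure.

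**4. Can it be carried over to QALYs?** Again no, because no QALY SD is given. Trapezoid weights for days 0, 42, 91, 182 and 365 are 0.058, 0.125, 0.192, 0.375 and 0.251. A difference of 0.05 present from 6 weeks onward gives 0.05 × (1 − 0.058) = 0.047 QALY. A linear build-up to 0.05 at 1 year gives 0.025 QALY. Power at 68 against 42 then depends on the SD assumed:

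| QALY difference | 1-year SDs reused as QALY SDs | Equal SDs at each visit, between-visit correlation 0.5 to 0.9 |
|---|---|---|
| 0.047 | 86% | 97% to 89% |
| 0.025 | 37% | 53% to 39% |

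These figures show only how far the answer depends on assumptions. Larger SDs at early visits would lower them. The early recovery and return to work described in sections 3.1 and 3.2 make the slow build-up the less natural case.

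**The case against.** The best defence is that the comparison is planned and only its test is unnamed. Section 10.4.2 evaluates the Touch-RSI QALY gain and forms the ICER, section 4.3 promises to compare patient-reported outcomes between groups, and section 4.1 includes a non-comparative aim, quality of life after Touch surgery, which the paired test serves. Naming a test or interval for the QALY difference can be left to an SAP. The 5% level in 10.4.2 stands in its own paragraph with the single-look statement and reads as a general rule.

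Much of this stands. A reader might infer that the study plans no comparison with RSI; the text does not support that. A reader might also infer that the 5% level is reserved for the paired test; it is not, and section 10.2 sets the same level for the two-sample comparison. Nor do the documents support saying that the paired test is almost certain to succeed, or that power on the QALY scale is lower than 90%: both depend on inputs the protocol does not give.

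What the defence does not answer is the contradiction. The protocol is not silent about a test. It names one as primary, in two places, and that test differs from the one used to justify the sample size and does not bear on the hypotheses in 10.1. An SAP that added the two-sample test would leave this conflict in the protocol.

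**Conclusion.** The point holds as a mismatch within the protocol: the power statement and the named primary test refer to different contrasts. This follows from the text alone and needs no assumption. The sample size itself is sound for the two-sample test, so aligning the analysis with 10.2 leaves power at 90.0% for 68 against 42 under the protocol's own means and SDs.

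Two limits apply. First, restoring the two-sample test makes the analysis agree with 10.2, but it does not test the cost-effectiveness hypothesis in 10.1, which concerns the ICER. A reader might take a significant EQ-5D-5L difference as confirming that hypothesis; it would not. Second, no power figure for the paired test or for QALYs should be quoted except as a range with its assumptions.

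**What to change.** - **Section 10.4.2 and synopsis:** make the Touch-RSI difference in 1-year EQ-5D-5L the primary quality-of-life analysis, using the two-sample unequal-variance test of 10.2 with a 95% CI.
- **Section 10.4.2:** report the Touch-RSI QALY difference with its 95% CI alongside the ICER.
- **Section 10.4.2 and synopsis:** relabel the paired t-test as a supportive analysis within the Touch group.
- **Section 10.4.1:** state that the comparative analyses also include the 42 RSI patients.
- **Section 10.2:** add that the 90% power refers to the 1-year EQ-5D-5L difference and not to QALYs or to the ICER hypothesis in 10.1.

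The cost is protocol wording and one additional analysis. No patients are added: the target stays at 68 evaluable and 80 enrolled. The synopsis says the RSI outcome data are already available. The protocol does not give the RSI visit schedule, so the sponsor should confirm that the RSI utilities were collected at time points that allow a comparable QALY.

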7 STUDY POPULATION

7.1 Eligibility criteria

Participants fulfilling all of the following inclusion criteria are eligible for the study:

- Informed Consent as documented by signature (Appendix Informed Consent Form)
- Patient is diagnosed with primary osteoarthritis (OA) at the thumb carpometacarpal (CMC I) joint and will be operated with a Touch® prosthesis
- Patient is working in Switzerland and intends to continue doing so for at least the duration of their study participation (1 year)
 - Comparison group: Patients who received a resection arthroplasty in a previous study (KEK-ZH Nr. 2013-0381) and had an occupation at that time

The presence of any one of the following exclusion criteria will lead to exclusion of the participant:

- Patient with any type of revision surgery at the CMC I joint
- Patient with rheumatoid arthritis
- Patient has an additional surgery in the same session (except for simultaneous trigger finger release at the thumb)
- Non-working patients
- Legal incompetence
- German or English language barrier which prevents the study participant from completing the questionnaires

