7.3 Assignment to study groups

All patients who fulfil the inclusion criteria will be considered for the study. Since this study utilises data of a previous study for the comparison group all the recruited participants will be assigned to the intervention group.

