9.2.2 Baseline

Demographics, medical history and information about the hand condition are obtained. The patient questionnaires (work situation, WPAI, brief MHQ, EQ-5D-5L, complications, expectations) are completed directly online (eCRFs) or on paper CRFs before surgery. Before surgery, the patients will also be clinically examined (range of motion, muscle strength, Kapandji-index, key pinch strength, grip strength). This is usually done by the surgeon during the preoperative consultation as well as shortly before the operation by a study assistant. Since right after the consultation the study assistant will inform the patients about the study in more detail anyways, she will also already clinically examine the patients. As the operations are typically scheduled in the following 2 months, there is thus no need for an additional clinical examination right before the operation. In the rare occasion a patient can't be operated in the next two months, the patient will again be clinically examined shortly before the surgery so as to keep the data up to date. Data will be electronically entered into eCRFs. The twofold measurement of clinical patient data is routinely done in our clinic, reduces the measuring bias of the surgeons and allows for more complete data sets.

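### The primary ICER uses an unadjusted Touch-minus-RSI QALY difference against a historical, non-randomised control group, with no step to make the groups comparable on utility

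*Protocol*

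**What the plan says.** Section 10.4.2 obtains each patient's QALYs by weighting utilities by time. It then fixes the primary estimator: "The incremental cost-utility ratio will be calculated as the difference in costs over the difference in Quality-Adjusted Life Years (QALYs) between both interventions". The printed formula is cost Touch minus cost RSI, divided by QALYs Touch minus QALYs RSI. The same section says "The gain in QALYs of Touch patients compared to RSI patients will be evaluated".

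The groups are not randomised. Section 7.3: "Since this study utilises data of a previous study for the comparison group all the recruited participants will be assigned to the intervention group".

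Section 7.1 words the work criterion differently for the two groups:
- Touch: "Patient is working in Switzerland and intends to continue doing so for at least the duration of their study participation (1 year".
- RSI: "Patients who received a resection arthroplasty in a previous study (KEK-ZH Nr. 2013-0381) and had an occupation at that time".

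EQ-5D-5L is collected pre-operatively in the Touch group. Section 9.2.2: "The patient questionnaires (work situation, WPAI, brief MHQ, EQ-5D-5L, complications, expectations) are completed directly online (eCRFs) or on paper CRFs before surgery". The one analysis that names the pre-operative utility as such is the paired t-test of change to 1 year in Section 10.4.2, which is a within-patient comparison.

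The mixed model in Section 10.4.3 names only time as an effect. The sensitivity analyses in Section 10.4.2 vary assumptions about QALY gain, indirect costs and direct costs, and name no confounder. The Synopsis (Study Product / Intervention) mentions retrospective matching, but only for the RSI patients who supply cost data, and names no matching variables.

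**The concern.** A difference in group means estimates a treatment effect only if the groups would have had the same QALYs under the same treatment. Here one group is prospective and the other comes from an earlier study. Touch patients must plan to stay in work for the year, while RSI controls only had to have a job at the time. Such a criterion could select for health, age or type of work.

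Baseline utility reaches the QALY in two ways: directly, as the first point of the utility curve, and indirectly, because patients who start higher tend to stay higher. With the estimator as printed, any pre-operative difference passes into the ICER denominator as if the implant had caused it. The expected denominator is small, so a small absolute shift can change the ratio substantially.

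**Working it through.** **1. The plan's own figure.** Section 10.2 gives RSI n = 42, mean 0.91, SD 0.09; Touch mean 0.96, SD 0.05; two-sided alpha 0.05; power 0.90; Satterthwaite t test.

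- Variance terms: 0.09²/42 = 0.0001929 and 0.05²/68 = 0.0000368. SE = √0.0002296 = 0.01515.
- Noncentrality: 0.05/0.01515 = 3.30, with about 57 degrees of freedom.
- Power by the noncentral t distribution: 0.9003 with 68 Touch patients, 0.8997 with 67. So 68 reproduces.
- 68/0.85 = 80, which also reproduces.

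The sample size is correct for its inputs. It rests on the same unadjusted contrast between cohorts.

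**2. Weight of baseline in the QALY.** The visit days in Section 9.1 are 0, 42, 91, 182 and 365. The protocol names no interpolation rule, so the trapezoid rule is assumed, on the Touch schedule because the RSI time points are not listed. The baseline weight is w₀ = 42/(2 × 365) = 0.0575. The later visits carry 0.1247, 0.1918, 0.3753 and 0.2507, which sum to 0.9425.

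**3. Shift in the raw QALY difference.** Let b be the baseline utility gap (Touch minus RSI) and β the slope of follow-up utility on baseline, taken as equal at all visits. Neither is in the protocol; both are assumptions.

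Shift in total QALYs = b × [w₀ + β(1 − w₀)]

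If gain in QALYs means QALYs above each patient's own baseline, b is subtracted once more:

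Shift in baseline-subtracted QALYs = −b × (1 − β)(1 − w₀)

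| b | β | Shift, total QALYs | Shift, baseline-subtracted |
|---|---|---|---|
| 0.01 | 0.3 | 0.0034 | −0.0066 |
| 0.01 | 0.5 | 0.0053 | −0.0047 |
| 0.02 | 0.3 | 0.0068 | −0.0132 |
| 0.02 | 0.5 | 0.0106 | −0.0094 |
| 0.05 | 0.3 | 0.0170 | −0.0330 |
| 0.05 | 0.5 | 0.0264 | −0.0236 |

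Example: 0.05 × (0.0575 + 0.5 × 0.9425) = 0.0264. Under either reading the shift is zero only if b is zero or, for baseline-subtracted QALYs, if β = 1.

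**4. What shifts of this order do.**

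- With the Section 10.2 SDs, 42 vs 68 patients and no true effect, a spurious 1-year utility difference of 0.01, 0.02 or 0.03 makes the sample-size test reject in about 10%, 25% or 49% of cases instead of 5%.
- At an assumed extra cost of 2,000 per patient, a QALY difference of 0.05 gives an ICER of 2,000/0.05 = 40,000, and 0.03 gives 2,000/0.03 = 66,667. Currency aside, this crosses the lower end of the range of 50,000 to 150,000 USD quoted in Section 3.1.

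**The case against.** The best reply is that covariate choice belongs in a statistical analysis plan and that Section 10.4.2 prints only the textbook ICER. The formula would accept adjusted means, and the section never calls the difference unadjusted. That is fair as far as it goes: that the difference is raw is inferred from the formula and from the absence of any adjustment for utilities elsewhere. But the protocol itself fixes the primary estimator of a historical-control comparison, and applied as printed it subtracts plain group quantities.

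Four stronger readings are tempting, and the document does not support them:

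- *That nothing at all is done about comparability.* The Synopsis plans matching for the RSI cost patients. It does not extend to QALYs.
- *That baseline adjustment is known to be feasible.* Baseline EQ-5D-5L is documented only for Touch. For RSI, the protocol says outcome data exist and plans QALYs for each patient, which implies earlier utilities, but it reports only a 1-year mean. Age, sex and working hours in the controls are not documented either.
- *That the earlier study's eligibility was looser throughout.* Its full criteria are not shown. Only the work wording in Section 7.1 demonstrably differs, and both groups are described as working.
- *That a known fraction of the planned QALY effect is bias, in Touch's favour.* The 0.05 in Section 10.2 is a 1-year utility difference, not a QALY difference. No baseline mean is given for either group, so neither size nor sign is known. If gain means baseline-subtracted QALYs, the sign reverses.

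**Conclusion.** The point holds in this form: the primary QALY contrast is a plain difference between non-randomised, non-concurrent groups, and no planned step makes them comparable on utility. For baseline gaps of 0.01 to 0.05 and slopes of 0.3 to 0.5, the raw difference in total QALYs shifts by about 0.003 to 0.026. Reading gain as baseline-subtracted reverses the direction without removing the bias.

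This range rests on an assumed gap, an assumed common slope, the trapezoid rule and the Touch visit schedule. It shows what an imbalance would do, not that one exists. The sample size is not in error. The change should be made before analysis, because the method in the plan is weaker than one that may be available at little cost.

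**What to change.** In Section 10.4.2:

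1. Confirm and state whether baseline EQ-5D-5L is held for the 42 RSI controls, and at which time points.
2. If it is, estimate the QALY difference by regression on group with baseline utility, plus whichever of age, sex and weekly working hours are held in both cohorts. Use this adjusted difference in the ICER and report the raw difference as secondary.
3. State whether QALY gain means total or baseline-subtracted QALYs.
4. For indirect costs, adjust for covariates held in both outcome cohorts. For direct costs, which Section 5.1 takes from a separate concurrent RSI cohort, adjust or match on pre-operative covariates held there, and name them.
5. Base any sensitivity analysis that restricts the controls on pre-operative criteria only. Selecting controls by employment at 1 year would condition on post-surgical status in one group, while Touch patients qualify on pre-operative intention.
6. State that adjustment does not remove period effects or unmeasured selection.

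If the RSI baseline data exist, the cost is wording and analysis time, with no new patients. For an assumed baseline correlation of 0.3 to 0.5, the standard error is multiplied by √(1 − 0.3²) = 0.954 to √(1 − 0.5²) = 0.866. Power for the 1-year utility contrast with 42 vs 68 patients then rises from 0.900 to about 0.925 to 0.963. This ignores the precision lost if the groups do differ at baseline. If the data do not exist, the protocol should say that the QALY contrast cannot be adjusted for baseline utility and carry that limitation into the interpretation of the ICER.

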10.4.3 Secondary Analysis

Categorical outcomes (e.g. radiological findings) will be described by proportions and frequency counts at follow-up time points.

Continuous outcomes (e.g. Brief MHQ or Pain) will be analysed by mixed model considering the effect of time and reported per examination time by their mean and standard error.

Cost-effectiveness analysis

The incremental cost-effectiveness ratio (ICER) will be calculated as:

Cost _{Touch®} - Cost _{RSI Arthroplastik} ADL pain score_{Touch®} - ADL pain score_{RSI Arthroplastik}

Costs will combine direct (inpatient and outpatient) and indirect (productivity losses) costs.

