4.3 Secondary Objective

As a secondary objective we want to determine whether direct medical costs are higher with the Touch® implant compared to RSI arthroplasty. Cost-effectiveness regarding pain ADL will be evaluated as the difference in costs over the difference in pain ADL between both interventions. We will analyse return to work after surgery in both groups. Lastly, we will compare the clinical and patient-reported outcomes after surgery for both groups.

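### Section 10.4.3 specifies a time-only mixed model, so it does not give the Touch versus RSI comparison of clinical and patient-reported outcomes set as an objective in Section 4.3

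*Protocol*

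**What the plan says.** Protocol Section 4.3 closes the list of secondary objectives with: "Lastly, we will compare the clinical and patient-reported outcomes after surgery for both groups". Section 8.1.2 and the synopsis add that outcome data for the RSI group already exist from a previous study and are to serve as the comparator. Section 7.3 confirms that no concurrent outcome control is recruited: "all the recruited participants will be assigned to the intervention group".

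The analysis of these outcomes is in Section 10.4.3. For continuous measures: "Continuous outcomes (e.g. Brief MHQ or Pain) will be analysed by mixed model considering the effect of time and reported per examination time", the summaries being a mean and a standard error. For categorical measures: "Categorical outcomes (e.g. radiological findings) will be described by proportions and frequency counts at follow-up time points". The section then gives one formula, a cost-effectiveness ratio with the cost difference between Touch and RSI in the numerator and the difference in pain during daily activities in the denominator.

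**The concern.** The objective is comparative and the model is not. A mixed model whose only named effect is time estimates how an outcome moves from visit to visit. It has no parameter for the difference between the two operations. Followed as written, the analysis would show that brief MHQ, pain, strength and motion change after surgery. It would not show whether Touch patients do better or worse than RSI patients, or with what precision.

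This matters more here than in a randomised trial. The control is an earlier cohort, so baseline differences between the groups are not balanced by design. If the protocol does not fix how the groups are contrasted and adjusted, that choice is left until the data are in hand.

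**Working it through.** **1. The plan's own figure.** The only sample-size calculation, in Section 10.2, is a between-group one. Inputs: RSI n = 42, mean 0.91, SD 0.09; Touch mean 0.96, SD 0.05; two-sided alpha 0.05; power 0.90; unequal-variance t test.

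- SE with 68 Touch patients = √(0.09²/42 + 0.05²/68) = √(0.0001929 + 0.0000368) = 0.01515.
- Difference / SE = 0.05 / 0.01515 = 3.30, with about 56.9 Satterthwaite degrees of freedom.
- Power from the noncentral t distribution is 0.8997 at 67 and 0.9003 at 68, so 68 is the minimum, as stated.
- Dropout: 68 / 0.85 = 80, as stated.

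The figure reproduces. The point does not depend on it, but it shows that the study was sized for a Touch versus RSI contrast.

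**2. Objective against analysis.**

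| Item | Section 4.3 | Section 10.4.3 |
|---|---|---|
| Question | Difference between groups | Course over time |
| Effects named | Group (implied) | Time |
| Reported | Comparison | Mean and standard error per visit |
| Categorical outcomes | Comparison | Proportions and counts |

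**3. What a time-only model estimates.** Write it as y(i,t) = μ + τ(t) + b(i) + e(i,t), where b(i) is the patient effect. The estimable contrasts are differences among the τ(t), that is, changes between visits. The group difference at visit t would be γ + δ(t), where γ is a group effect and δ(t) a group-by-visit effect. Neither is in the model. There are three ways to run it:

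- Touch patients only: change in Touch, with no comparator.
- Both groups pooled: one mean per visit, averaging over the operations. For illustration only, with the Section 10.2 figures (EQ-5D-5L is not an outcome that 10.4.3 names for this model), the pooled 1-year mean would be (42 × 0.91 + 68 × 0.96) / 110 = 103.5 / 110 = 0.94. The assumed difference of 0.05 would not be visible.
- Each group separately: two sets of means and standard errors, with the unadjusted difference left for the reader to form.

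**4. Is it an isolated shorthand?** Section 10.4.2 follows the same pattern: the change in EQ-5D utility from before surgery to 1 year is tested by a paired t test within patients, although Section 10.2 sizes the study on a two-sample test. The between-group quantities that 10.4 does name are the QALY gain, the cost-utility ratio and the pain cost-effectiveness ratio.

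**5. Which outcomes are affected.** The continuous or score-type measures in Section 5.2 are range of motion including the Kapandji index, grip strength, key pinch, brief MHQ, and pain at rest and during daily activities. Only the last enters a between-group expression in 10.4.3, and there as the denominator of a ratio rather than as a difference with its own interval.

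**The case against.** The best defence is that 10.4.3 names time without saying that group is left out. Full model terms, covariates and contrasts are often placed in a separate SAP, which was not available here. Sections 4.3 and 8.1.2 make the intention to compare clear, and RSI data are available. Part of this stands: the documents do not show that the comparison cannot be made, only that the stated analysis does not make it. It does not remove the point. The protocol is not silent: it names the model, the effect and the reporting format, and these answer a different question. Section 10.4.6 also treats 10.4 as the statistical plan, from which deviations need justification.

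Three stronger readings are tempting, and the documents do not support them.

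- **That the analysis set blocks or biases the comparison.** For secondary outcomes Section 10.4.1 uses "all eligible and enrolled patients that effectively received the respective intervention according to the CIP will be included", whereas the main dataset is "all eligible and enrolled patients that will be operated and scheduled to receive the Touch® prosthesis". A set of treated patients can still be compared with RSI. The reference to the respective intervention suggests that both groups were meant, and Section 7.1 defines the RSI group by the operation received. The treated set therefore matches the comparator.
- **That no between-group result is produced at all.** The pain ratio in 10.4.3 contains two between-group differences, and 10.4.2 compares QALYs and costs.
- **That a cost-per-QALY error follows.** The protocol gives neither a rate nor a cost of conversion to another procedure, and the main cost-utility ratio rests on the scheduled set. No such figure can be derived.

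**Conclusion.** The point holds in a limited form. For clinical and patient-reported outcomes, the analysis in Section 10.4.3 yields change over time and no Touch minus RSI difference, while Section 4.3 promises that comparison. Apart from pain during daily activities, which enters a ratio, no continuous secondary outcome in Section 5.2 has a between-group quantity in 10.4.3. No numerical bias is attached, and the main cost-utility ratio is unaffected.

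The conclusion assumes that 10.4.3 is applied as worded. If a separate SAP already names a group effect, what remains is an inconsistency to be aligned in the protocol. It should be corrected, but it concerns secondary objectives and does not threaten the primary analysis.

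**What to change.** Amend Section 10.4.3 so that each continuous secondary outcome is analysed by a mixed model with group, visit, group-by-visit and the baseline value of the outcome as fixed effects, and patient as random effect. With baseline as a covariate, the responses are the post-operative visits. Measures with no pre-operative value, such as satisfaction, go without that term. Report the Touch minus RSI difference with a 95% confidence interval at each visit and for each outcome that the RSI cohort also has. The time course within each group can still be shown from the same model.

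The protocol should list which measures and visits the RSI dataset contains, since it says only that outcome data exist. Outcomes or visits without an RSI counterpart should be labelled as descriptive for Touch.

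Cost: an amendment of wording and slightly more analysis work, with no new data for the measures both cohorts share. The limits are that the comparison covers only those shared measures and visits, and that adjusting for the baseline value reduces but does not remove confounding from a historical, non-randomised control.
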